#### ***2.1.4.1 Adverse events variables***

Adverse events (including serious adverse events [SAEs], and AEs of special interest) are recorded from the time of signed informed consent until the end of study. All AEs diagnosed by the Investigator, including CV events (irrespective of the result of the adjudication), will be reported and described.

All AEs will be coded to a “lowest level term (LLT)”, “preferred term (PT)”, “high level term (HLT)”, “high level group term (HLGT)”, and associated primary “system organ class (SOC)” using the version of MedDRA currently in effect at Sanofi at the time of database lock.

### ***Adverse event observation period***

Pretreatment adverse events are adverse events that developed or worsened or became serious from the signed informed consent date up to first administration of IMP.

Treatment-emergent adverse events are adverse events that developed or worsened or became serious during the treatment-emergent adverse event period.

Post-treatment adverse events are adverse events that developed or worsened or became serious during the post-treatment period.

### ***Grouping of adverse events (including adverse event of special interest)***

Adverse events of special interest (AESI) are AEs (serious or non-serious) that need to be monitored, documented, and managed in a pre-specified manner described in the protocol. More generally, below are the grouping of adverse events that will be analyzed

- Alanine aminotransferase (ALT)  $\geq 3$  upper limit of normal range (ULN) (if baseline ALT<ULN) or ALT  $\geq 2$  times the baseline value (if baseline ALT  $\geq$ ULN), selected using laboratory data;
- Allergic events:
  - General allergic events, selected using SMQ “hypersensitivity” (broad and narrow) excluding the following preferred terms linked to local injection site reactions (“infusion site dermatitis”, “infusion site hypersensitivity”, “infusion site rash”, “infusion site urticaria”, “injection site dermatitis”, “injection site hypersensitivity”, “injection site rash”, “injection site urticaria”, and “injection site vasculitis”)
  - General allergic events and local allergic reactions at IMP injection site will be described. This selection will be based on the above selection for general allergic event and on the following selection of PT from the symptoms complementary form for local injection site reaction: “Injection site dermatitis”, “Injection site hypersensitivity”, “Injection site oedema”, “Injection site rash”, “Injection site urticaria”, “Injection site eczema”, “Injection site vasculitis”, “Injection site swelling”, “Infusion site dermatitis”, “Infusion site hypersensitivity”, “Infusion site oedema”, “Infusion site rash”, “Infusion site urticaria”, “Infusion site swelling”.
- Local injection site reactions, selected using e-CRF specific tick box on the AE page
- Hemolytic anemia, selected using e-CRF specific tick box on the AE page and confirmed final diagnosis provided in the AE complementary form;
- Neurologic events selected using a CMQ, based on SMQs “demyelination” (broad and narrow), “peripheral neuropathy” (broad and narrow), and “Guillain-Barre syndrome” (broad and narrow) excluding the following preferred terms “acute respiratory distress syndrome”, “asthenia”, “respiratory arrest” and “respiratory failure” and including selected PTs from SMQ “optic nerve disorders” (see [Appendix C Table 5](#) for the list of terms);
- Neurocognitive events:
  - Selected using a CMQ, based on the following 5 HLGTs: “deliria (including confusion)”, “cognitive and attention disorders and disturbances”, “dementia and amnestic conditions”, “disturbances in thinking and perception”, and “mental impairment disorders”
  - A second grouping of terms for neurocognitive events was defined based on Regulatory Agency request (see [Appendix C Table 6](#) for the list of terms)
- Ophthalmologic events selected using SMQs;

- Cataract using HLT “Cataract conditions”
- Overdose of IMP (symptomatic or asymptomatic), selected using appropriate MedDRA codes and the tick box “Overdose with IMP” in the adverse event complementary e-CRF form
- Pregnancy of female patient/subject (including male subject’s partner) selected using appropriate MedDRA codes;
- Hepatic disorder events using SMQ “Hepatic disorder”;
- Diabetes mellitus or diabetic complications selected using HLGT “diabetes complications” (including PTs pertaining to the secondary SOC included in the HLGT), HLT “diabetes mellitus”, and HLT “carbohydrate tolerance analyses (incl diabetes)” excluding PTs “blood glucose decreased” and “Glycosylated haemoglobin decreased” and including the PTs “hyperglycaemia”, “Hyperglycaemic unconsciousness” and “Hyperglycaemic seizure” from the HLT “Hyperglycaemic conditions NEC”;

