9.2.1 Adverse event

All AEs diagnosed by the investigator, irrespective of the result of the adjudication for CV events, will be reported and described.

All AEs will be coded to a “lowest level term (LTT)”, “preferred term (PT)”, “high level term (HLT)”, “high level group term (HLGT)” and associated primary “system organ class (SOC)” using the version of medical dictionary for regulatory activities (MedDRA) currently in effect at Sanofi at the time of the considered database lock.

AEs of clinical interest include the following:

- General allergic reactions (using special e-CRF pages, see [Section 10.4.5.1](#), [Section 10.4.5.2](#) and [Section 10.6.2](#))
- Local injection site reactions (using special e-CRF pages) (please refer to [Section 10.6.1](#))
- Hemolytic anemia (using special e-CRF pages, see [Section 10.4.5.1](#))
- Neurological (including neurocognitive) AEs (using special e-CRF pages, see [Section 10.4.5.1](#), and [Section 10.4.5.2](#))
- Ophtalmologic AEs (using special e-CRF pages, see [Section 10.4.5.1](#) and [Section 10.4.5.2](#))

Adjudicated CV events include all CV AEs positively adjudicated (see [Section 10.6.3](#)). The adjudication categories are the following:

- CHD death
- Non-fatal MI
- Fatal and Non-fatal ischemic stroke
- Unstable angina requiring hospitalization
- Congestive heart failure requiring hospitalization
- Ischemia-driven coronary revascularization procedure

In addition, the classification of all deaths will occur.

Adverse event observation period

The AE observations are per the observation periods defined above.

Death observation period

The death observations are per the observation period defined above. In addition, “post-study” death includes all deaths reported after the end of the study (see definition of end of study period per patient in [Section 6.2.1](#)).

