 - f) An overdose (accidental or intentional) is an event suspected by the Investigator or spontaneously notified by the patient (not based on systematic injection counts) and defined as at least twice the intended dose within the intended therapeutic interval (ie, 2 or more injections from the double-blind treatment kit are administered in <7 calendar days); to be reported using the corresponding screens in the e-CRF using

the Term ‘Symptomatic OVERDOSE (accidental [or intentional])’. The patient should be monitored and appropriate symptomatic treatment instituted.

- g) The circumstances of the overdose should be clearly specified in the verbatim.
 - Ezetimibe or placebo for ezetimibe:
 - a) An overdose (accidental or intentional) is an event suspected by the Investigator or spontaneously notified by the patient (not based on systematic capsule counts) and defined as at least twice the intended dose within the intended therapeutic interval (ie, 2 or more capsules from the double-blind treatment kit are administered within one calendar day); to be reported using the corresponding screens in the e-CRF using the Term ‘Symptomatic OVERDOSE (accidental [or intentional])’. The patient should be monitored and appropriate symptomatic treatment instituted.
- Neurological (including neurocognitive) Events
 - Neurological (including neurocognitive) Events that require additional examinations/procedures and/or referral to a specialist should be reported as an AESI with immediate notification.
- Ophthalmologic Events
 - Ophthalmologic Events that require additional examinations/procedures and/or referral to a specialist should be reported as an AESI with immediate notification.

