- Neurological (including neurocognitive) events
 - Any AEs related to neurological (including neurocognitive) abnormalities with the exception of those requiring additional examinations/procedures and/or referral to a specialist (as mentioned in [Section 10.4.5.1](#)) should be reported as AESI without immediate notification
- Ophthalmologic events
 - Any AEs related to ophthalmologic abnormalities with the exception of those requiring additional examinations/procedures and/or referral to a specialist (as mentioned in [Section 10.4.5.1](#)), should be reported as AESI without immediate notification

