11.4.3.1 Adverse events

Adverse event incidence tables will present by SOC (sorted by internationally agreed order), HLGT, HLT and PT sorted in alphabetical order for each treatment group, the number (n) and percentage (%) of patients experiencing an AE. Multiple occurrences of the same event in the same patient will be counted only once in the tables within a treatment phase. The denominator for computation of percentages is the safety population within each treatment group.

Adverse event incidence table will be provided by treatment group for all types of TEAEs: all TEAEs, all treatment emergent AESI (defined with a PT or a prespecified grouping), TEAE by maximal intensity, all treatment emergent SAEs and all TEAEs leading to permanent treatment discontinuation.

If any clinically significant signal is detected and need further characterization or for AE of clinical interest, exploration of time to onset will be performed for these selected TEAEs as described below to account for the differential exposure time in all patients.

Selected TEAEs will be also analyzed using time-to-event approach (Kaplan-Meier methodology). Time from the first dose of double-blind IMP injection to the first occurrence of

the event will be calculated (only the first event will be counted). Patients without any event will be censored at the end of the TEAE period.

Death: The following deaths summaries will be generated:

- Number (%) of patients who died by study period (TEAE, on-study, post-study) summarized on the safety population by treatment received
- Death in nonrandomized patients or randomized and not treated patients
- TEAE leading to death (death as an outcome on the AE CRF page as reported by the Investigator) by primary SOC, HLGT, HLT and PT showing number (%) of patients sorted by internationally agreed order of SOC and alphabetic order of HLGT, HLT, and PT.

Adjudicated cardiovascular events:

The number and percentage of patients experiencing a positively adjudicated CV event will be presented by treatment group overall and by category of adjudication.

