### ***Analysis of groupings of adverse event(s) including selected adverse events of special interest***

- All grouping of TEAEs including adverse events of special interest as listed in [Section 2.1.4.1](#) will be analyzed using selections defined in [Section 2.1.4.1](#) and will be presented by SMQ and PT (when selection is based on SMQs) and by SOC and PT (when selection is based on the e-CRF tick box or HLGT/HLT). The summaries will be sorted by decreasing incidence of PT within each SOC/SMQ (in the alirocumab group).
- Analyses of grouping of AEs for diabetes will be performed overall and according to the diabetic status at baseline.

In addition, the following variables will be tabulated for the local injection site reactions TEAEs:

- Intensity of the event (mild, moderate, severe);
- Number of events divided by the number of double-blind IMP injections received;
- Time from first double-blind IMP injection to first injection site reaction;
- Description of the highest intensity of each symptom recorded in the specific e-CRF page with table and bar chart.

Besides, description of symptoms and possible etiologies for General Allergic Reaction TEAE reported by investigator (using the tick box), will be presented.

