**Table 5 – Selected PTs from SMQ “Optic nerve disorders” including in the CMQ for neurologic events**

MedDRA Term Label	Preferred Term Code
Benign neoplasm of optic nerve	10057424
Optic atrophy	10030910
Optic discs blurred	10030923
Optic nerve disorder	10061322
Optic nerve injury	10030938
Optic nerve neoplasm	10053645
Optic nerve operation	10053272
Optic neuropathy	10061323
Papillitis	10033708
Pseudopapilloedema	10037141

MedDRA Term Label	Preferred Term Code
Subacute myelo-opticoneuropathy	10058009
Toxic optic neuropathy	10044245
Visual evoked potentials abnormal	10047549
Amaurosis fugax	10001903
Blindness	10005169
Blindness unilateral	10005186
Colour blindness acquired	10010051
Colour vision tests abnormal	10010056
Cranial nerve injury	10061094
Delayed myelination	10076456
Fundoscopy abnormal	10017520
Hemianopia	10019452
Hemianopia heteronymous	10019455
Hemianopia homonymous	10019456
Loss of visual contrast sensitivity	10064133
Neuro-ophthalmological test abnormal	10029256
Night blindness	10029404
Ophthalmological examination abnormal	10056836
Optic pathway injury	10030949
Optical coherence tomography abnormal	10073561
Quadranopia	10075427
Visual acuity reduced	10047531
Visual acuity reduced transiently	10047532
Visual acuity tests abnormal	10047534
Visual field defect	10047555
Visual field tests abnormal	10047567
Visual impairment	10047571
Visual pathway disorder	10061411

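### The SAP's neurologic and ophthalmologic AESI rows are MedDRA selections that do not match the protocol's AESI definition, and no table counts what investigators reported as those AESIs

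*SAP*

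**What the plan says.** Protocol 9.2.1 lists, among the AEs of clinical interest, "Neurological (including neurocognitive) AEs (using special e-CRF pages, see" Sections 10.4.5.1 and 10.4.5.2. Ophthalmologic AEs are listed the same way.

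The two reporting sections divide these events by what the case needed:
- 10.4.5.1: "Neurological (including neurocognitive) Events that require additional examinations/procedures and/or referral to a specialist should be reported as an AESI with immediate notification".
- 10.4.5.2 takes the remainder, "Any AEs related to neurological (including neurocognitive) abnormalities with the exception of those requiring additional examinations/procedures and/or referral to a specialist", as AESIs without immediate notification.

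Parallel text covers ophthalmologic events. Protocol Appendix C asks for a specific form in all four cases. Protocol 11.4.3.1 plans incidence tables that include "all treatment emergent AESI (defined with a PT or a prespecified grouping").

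The SAP's entry in 2.1.4.1 reads: "Neurologic events selected using a CMQ, based on SMQs". The SMQs are demyelination, peripheral neuropathy and Guillain-Barre syndrome, each broad and narrow. Four preferred terms are removed, and selected terms from the optic nerve disorders SMQ (Appendix C Table 5) are added. Neurocognitive events have separate rows, one from five HLGTs and one from Appendix C Table 6. For the eye the entry is "Ophthalmologic events selected using SMQs", with no SMQ named; cataract has its own row. SAP 2.4.5.1 then specifies the tables: "All grouping of TEAEs including adverse events of special interest as listed in" Section 2.1.4.1 are analyzed with the selections given there. SAP 1.5 reports no major changes from the protocol's statistical section.

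**The concern.** The protocol defines a neurological AESI by the investigator's judgment, with no limit by MedDRA term. The SAP defines the row of nearly the same name by a short list of disease-specific queries. Someone reading that row in the study report would reasonably take it as the protocol's neurological AESI, and it is not.

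This matters because of what the AESI is for. Protocol Section 4 promises further monitoring for adverse events associated with low LDL-C. Its account of earlier patients with very low LDL-C names neurological effects first. Sites are asked to fill in dedicated pages for these events, and to report within 24 hours the cases that need work-up or referral. Under the SAP, neither the number of such reports nor the split by notification type is tabulated by arm.

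**Working it through.** There is no figure to reproduce and no arithmetic to do. The check is to set the protocol's definition beside each SAP selection.

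1. **Protocol scope.** Under 10.4.5.1, neurological events needing additional examinations, procedures or referral are AESIs. Under 10.4.5.2, all others are AESIs. The two sets are complementary, so their union is every neurological AE, neurocognitive ones included. The same reasoning gives every ophthalmologic AE.

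2. **SAP scope, neurologic row.** Three SMQs, minus four preferred terms (acute respiratory distress syndrome, asthenia, respiratory arrest, respiratory failure), plus Table 5. Table 5 has 38 preferred terms. Nearly all are optic or visual, for example "Visual acuity reduced"; the exceptions include cranial nerve injury and delayed myelination. There is no row for the nervous system SOC as a whole and none based on the neurological e-CRF page.

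3. **SAP scope, neurocognitive rows.** The five HLGTs cover delirium, cognition and attention, dementia and amnesia, thinking and perception, and mental impairment. Table 6 stays within that field. These rows account for the neurocognitive part of the protocol's AESI, not for the other neurological events outside the three SMQs.

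4. **SAP scope, ophthalmologic row.** SMQs are used but not identified, so how closely the row matches the protocol's AESI cannot be judged. It is not form-based.

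5. **What the AESI tables are built from.** SAP 2.4.5.1 uses only the 2.1.4.1 selections. An event reported as a neurological AESI whose term lies outside steps 2 and 3 therefore has no neurologic or neurocognitive AESI row. In the other direction, a visual term from Table 5 enters the neurologic row even if the site reported it as ophthalmologic.

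6. **Whether form-based selection is foreign to the SAP.** It is not. In 2.1.4.1, local injection site reactions are selected by an e-CRF tick box, hemolytic anemia by a tick box plus a confirmed diagnosis on the complementary form, and overdose partly by a tick box. The tick box for general allergic reactions is a weaker precedent, because 2.4.5.1 uses it only to describe symptoms and possible causes.

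7. **Whether the narrowing is disclosed.** Neither SAP 1.5 nor 1.6 mentions it, and 2.1.4.1 does not call the row a subset.

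**The case against.** The case for leaving the SAP alone has four parts.

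- **The method is permitted.** Protocol 11.4.3.1 allows AESIs to be tabulated by a prespecified grouping, and a CMQ is one. SAP 2.1.4.1 also presents its list as the groupings to be analyzed more generally, without claiming that each row reproduces every form submitted. This stands as a defense of having a CMQ row. It does not supply a table of all AESIs when the grouping covers only part of one.

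- **Nothing goes unreported.** All TEAEs are tabulated by SOC, HLGT, HLT and PT for each arm, and so are serious TEAEs and those leading to discontinuation. Similar TEAE summaries are planned, if applicable, for patients with two consecutive LDL-C values below 25 mg/dL. This stands. A reader might infer that a between-arm difference would be scattered over single preferred terms and missed. The documents do not support that, because these tables aggregate well above the preferred term.

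- **Examples depend on term lists that are not in the documents.** A reader might infer that a seizure reported as an AESI would appear in no AESI table. No seizure term is named in the neurologic or neurocognitive rules or in Tables 3 to 6; hyperglycaemic seizure appears only in the diabetes grouping. But SMQ contents are not given, and names are a poor guide to them: the SAP has to remove asthenia and three respiratory terms from queries whose titles do not suggest them. Any single example must be checked in MedDRA.

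- **Form-based rows are noisier.** They will pick up common non-specific terms. That is true, and it is a reason to show them beside the standardized selection and not in its place.

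**Conclusion.** The point holds as a mismatch of scope and labelling between protocol and SAP. The neurologic row is narrower than the protocol's neurological AESI, the ophthalmologic row has an unspecified relation to its counterpart, and neither is disclosed. No planned table counts these AESIs as reported, or shows which needed work-up or referral.

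The consequence is limited. Collection is complete, the events are counted by arm in the general and serious TEAE tables, safety is descriptive with no formal testing, and efficacy is unaffected. The number of patients involved cannot be estimated, because the documents give neither a rate of neurological AEs nor the share that the CMQ would capture.

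The conclusion rests on one assumption: that three SMQs named for specific disorders do not between them span all neurological AEs. It does not depend on any particular term lying outside them. The change is worth making because it is cheap and gives the safety objective a count that matches the protocol's own definition.

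**What to change.** In SAP 2.1.4.1, before database lock:

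- Keep the CMQ and SMQ rows. State that the neurologic CMQ is a prespecified subset of the protocol's neurological AESI, and name the ophthalmologic SMQs.
- Add two selections: neurological (including neurocognitive) AESIs and ophthalmologic AESIs, each as reported on the special e-CRF pages. Tabulate both by SOC and PT and by arm, with and without immediate notification, following the tick-box selection already used for local injection site reactions and hemolytic anemia.
- Confirm which e-CRF field carries the notification type. Protocol Appendix C requires the Safety Complementary Form both for immediate-notification AESIs and for any serious event, so that form alone may not separate the two.
- Check in the MedDRA version used whether terms of interest, such as seizure, fall inside the named SMQs.

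The cost is a few lines of SAP text and two descriptive tables from data already collected. The new tables will contain common non-specific terms and should be read with that in mind.

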### ***Cardiovascular events***

Suspected CV events that occur from randomization until the follow up visit will be submitted to the Clinical Events Committee (CEC) for adjudication.

Adjudicated CV events include all CV AEs positively adjudicated as defined in the Clinical Events Committee charter. The following categories will be described:

- CHD death;
- Non-fatal MI;
- Fatal and non-fatal ischemic stroke;
- Unstable angina requiring hospitalization;
- Congestive heart failure requiring hospitalization;
- Ischemia driven coronary revascularization procedure.

#### ***2.1.4.2 Deaths***

The deaths observation period are per the observation periods defined below.

- Death on-study: deaths occurring during the on-study observation period;
- Death on-treatment: deaths occurring during the treatment-emergent adverse event period;
- Death post-study: deaths occurring after the end of the study.

#### ***2.1.4.3 Laboratory safety variables***

Clinical laboratory data consists of blood analysis, including hematology, clinical chemistry, and urinalysis. Clinical laboratory values after conversion will be analyzed into standard international units and will be used in all listings and tables.

Unless otherwise specified, blood samples for clinical laboratories will be taken at Visit 1 (Week -3), Visit 3 (Week 0), Visit 6 (Week 12), Visit 8 (Week 24), or early termination, and

during the follow-up visit (Visit 9 [Week 32]) in case of abnormality unless otherwise specified. The laboratory parameters will be classified as follows:

- Hematology:
  - Red blood cells and platelets: hemoglobin, hematocrit, erythrocytes count, platelets count, reticulocyte count, red blood cell distribution width (RDW);
  - White blood cells: white blood cell count, neutrophils, lymphocytes, monocytes, basophils, eosinophils.
- Clinical chemistry:
  - Metabolism: glucose, total protein, albumin, creatine phosphokinase;
  - Electrolytes: sodium, potassium, chloride, calcium, phosphorus, bicarbonate;
  - Renal function: creatinine, eGFR, blood urea nitrogen, uric acid;
  - Liver function (also measured at Week 4, Week 8, and Week 16, except gamma glutamyl transferases [GGT] and lactate dehydrogenase [LDH]): ALT, aspartate aminotransferase (AST), alkaline phosphatase (ALP), GGT, total bilirubin, and in case of total bilirubin values above the normal range, must include direct and indirect bilirubin, LDH.
- Hepatitis screen: anti-hepatitis-C antibody (Ab) (at Week -3 and Week 24/or early termination).

Technical formulas are described in [Section 2.5.1](#).

